3.1.2. Exclusion Criteria

- 1. Patients with endometrioid, clear cell, mucinous, or sarcomatous histology, mixed tumors containing any of the above histologies, or low-grade/borderline ovarian tumor
- 2. Patients with prior wide-field radiotherapy (RT) affecting at least 20% of the bone marrow
- 3. Patients with > Grade 1 peripheral neuropathy per Common Terminology Criteria for Adverse Events (CTCAE)
- 4. Patients with active or chronic corneal disorders, history of corneal transplantation, or active ocular conditions requiring ongoing treatment/monitoring, such as uncontrolled

Document ID: CLIN-00067	Title: IMGN853-0419 Clinical Study Protocol	Version: 2.0
Legacy ID: 26587		Approved Date: 12/22/202

glaucoma, wet age-related macular degeneration requiring intravitreal injections, active diabetic retinopathy with macular edema, macular degeneration, presence of papilledema, and/or monocular vision

5. Patients with serious concurrent illness or clinically relevant active infection, including, but not limited to the following:
 - a. Active hepatitis B or C infection (whether or not on active antiviral therapy)
 - b. HIV infection
 - c. Active cytomegalovirus infection
 - d. Any other concurrent infectious disease requiring IV antibiotics within 2 weeks prior to the first dose of MIRV

Note: Testing at screening is not required for the above infections unless clinically indicated.

6. Patients with a history of multiple sclerosis (MS) or other demyelinating disease and/or Lambert-Eaton syndrome (paraneoplastic syndrome)
7. Patients with clinically significant cardiac disease including, but not limited to, any of the following:
 - a. Myocardial infarction \leq 6 months prior to first dose
 - b. Unstable angina pectoris
 - c. Uncontrolled congestive heart failure (New York Heart Association > class II)
 - d. Uncontrolled \geq Grade 3 hypertension (per CTCAE)
 - e. Uncontrolled cardiac arrhythmias
8. Patients with a history of hemorrhagic or ischemic stroke within 6 months prior to enrollment
9. Patients with a history of cirrhotic liver disease (Child-Pugh Class B or C)
10. Patients with a previous clinical diagnosis of noninfectious interstitial lung disease (ILD), including noninfectious pneumonitis
11. Patients requiring use of folate-containing supplements (eg, folate deficiency)
12. Patients with prior hypersensitivity to monoclonal antibodies (mAb)
13. Women who are pregnant or breastfeeding
14. Patients who received prior treatment with MIRV or other FR α -targeting agents
15. Patients with untreated or symptomatic central nervous system (CNS) metastases
16. Patients with a history of other malignancy within 3 years prior to enrollment

Note: patients with tumors with a negligible risk for metastasis or death (eg, adequately controlled basal-cell carcinoma or squamous-cell carcinoma of the skin, or carcinoma in situ of the cervix or breast) are eligible.
17. Prior known hypersensitivity reactions to study drugs and/or any of their excipients

Prospective approval of protocol deviations to recruitment and enrollment criteria, also known as protocol waivers or exemptions, is not permitted.

Document ID: CLIN-00067	Title: IMGN853-0419 Clinical Study Protocol	Version: 2.0
Legacy ID: 26587		Approved Date: 12/22/202

4. INVESTIGATIONAL PLAN

4.1. Study Design

4.1.1. Overview and Schema

This Phase 2 study is designed to evaluate the efficacy and safety of MIRV in patients with recurrent platinum-sensitive, high-grade serous EOC, primary peritoneal, or fallopian tube cancer, whose tumors express a high level of FR α . Patients will have had at least 2 prior lines of therapy. These will include at least 2 lines of platinum-containing therapy or 1 line with a documented platinum allergy. All patients will be, in the opinion of the Investigator, appropriate for non-platinum single-agent therapy for their next line of therapy. FR α positivity will be defined by the Ventana FOLR1 (FOLR1-2.1) CDx assay (Ventana FOLR1 Assay).

The study is designed to test the null hypothesis that the ORR is $\leq 28\%$ using an optimal Simon's two-stage design ([Simon 1989](#)) without a planned pause in enrollment given preliminary efficacy and established safety of MIRV. Approximately 75 patients will be enrolled so that a total of 69 patients will be efficacy evaluable.

Efficacy evaluable patients include those who have at least 1 measurable lesion (per RECIST v1.1) at baseline and received at least 1 dose of MIRV.

All patients will receive single-agent MIRV at 6 mg/kg AIBW ([Appendix D](#)) administered through IV infusion on Day 1 of every 3-week cycle (Q3W).

Computerized tomography (CT) or magnetic resonance imaging (MRI) scans will be collected for sensitivity analysis by BICR.

Patients will continue to receive MIRV until PD, unacceptable toxicity, withdrawal of consent, death, or until the Sponsor terminates the study (whichever comes first).

Tumor assessments, including radiological assessment by CT/MRI scans, will be performed at Screening and subsequently every 6 weeks (± 1 week) from Cycle 1 Day 1 (C1D1) for the first 36 weeks then every 12 weeks (± 3 weeks) until PD, death, the start of new anticancer therapy, or patient's withdrawal of consent, whichever occurs first.

Patients who discontinue MIRV for reasons other than progressive disease (PD) will continue with tumor assessments until documentation of PD or the start of a new anticancer therapy, whichever comes first. Prior to Week 36 (from C1D1), assessments should occur every 6 weeks (± 1 week) as allowed by local requirements but must occur at an interval of no more than 12 weeks. After Week 36, assessments will occur every 12 weeks (± 3 weeks) until documentation of PD per RECIST v1.1 or the start of new anticancer therapy.

All patients who discontinue MIRV will be followed for survival every 3 months (± 1 month) until death, lost to follow-up, withdrawal of consent for survival follow-up, or End of Study (EOS), whichever comes first. Additional survival follow-up calls may occur periodically, if needed.

Document ID: CLIN-00067	Title: IMGN853-0419 Clinical Study Protocol	Version: 2.0
Legacy ID: 26587		Approved Date: 12/22/202

4.1.2. Dose and Schedule for Mirvetuximab Soravtansine

MIRV will be administered at 6 mg/kg IV on Day 1 of every 3-week cycle (Q3W).

5. STUDY TREATMENT

5.1. Mirvetuximab Soravtansine

The investigational study drug, MIRV, will be provided by ImmunoGen, at a protein concentration of 5.0 mg/mL in an aqueous pH 5.0 buffered solution. See the Investigator Brochure for complete list of excipients.

5.1.1. Mirvetuximab Soravtansine Packaging

MIRV will be provided in a 20 mL glass, single-use Type I vial. The container closure for the Type I glass vials will consist of a 20 mm ethylene tetrafluoroethylene (ETFE)-coated serum stopper (Flurotec®) with a 20 mm aluminum TruEdge® seal with blue Flip-off® top.

Refer to the Pharmacy Manual for labeling and storage information.

5.1.2. Mirvetuximab Soravtansine Accountability

Specific details regarding storage and handling of MIRV can be found in the Pharmacy Manual. Accountability and shipping documents for MIRV must be maintained by the Principal Investigator (PI) or designee (eg, the study pharmacist). The Investigator or designee must maintain an accurate record of all MIRV received, stored, dispensed, destroyed, and used in an Investigational Product Dispensing/Accountability Log or equivalent. These records must always be available for inspection, and a copy will be supplied to ImmunoGen on request. Information recorded on the Accountability Log will include dates and quantities of drug received, dates and quantities of drug dispensed, patient number and initials to whom drug is administered, lot number of drug administered, the recorder's initials, and dates and quantities of drug destroyed or returned. Upon receipt, vials should be visually inspected for vial integrity (ie, cracks or leaks) and a record of any damaged or suspect drug should be kept on the Accountability Log.

Upon completion of the study, all MIRV dispatched to a site must be accounted for and unused supplies destroyed according to the site's standard operating procedures (SOPs) or returned to depot (refer to Pharmacy Manual). The original drug reconciliation records shall be maintained at the site and a copy collected and sent to ImmunoGen or designee once a representative of the company has confirmed the drug accountability.

Drug accountability will be monitored.

5.1.3. Mirvetuximab Soravtansine Study Treatment Compliance

MIRV supplied for the study may not be used for any purpose other than the study or administered other than as described in this protocol.

If necessary, MIRV from different drug lots may be mixed in a single-dose administration.

Document ID: CLIN-00067	Title: IMGN853-0419 Clinical Study Protocol	Version: 2.0
Legacy ID: 26587		Approved Date: 12/22/202

Under no circumstances is the Investigator allowed to release study drug supplies to any physician not named in the Food and Drug Administration (FDA) Form 1572 (or equivalent) to administer these supplies to a patient not enrolled in this study. If investigational supplies are to be dispensed from any facility other than that supervised directly by the PI (ie, hospital pharmacy, satellite pharmacy), it is the responsibility of the PI to ensure that all study drug is stored and administered as described (refer to Pharmacy Manual for instructions).

5.2. Assignment of Patient Number

Patient numbers are assigned in sequential order as patients sign the pre-screening informed consent to participate.

5.2.1. Enrolled Patient Definition

Patients who have consented to the study and have received at least 1 dose of study drug, are considered enrolled. Patients who are issued a patient number, but who do not successfully complete the screening process and are not treated will be considered screen failures. Patient numbers for patients who screen fail will not be re-issued.

5.2.2. Patient Assignment to Dosing Regimens

All patients will receive MIRV 6 mg/kg AIBW IV Q3W.

5.3. Blinding Methods

Not applicable as this is an open-label, single-arm study.

5.4. Study Treatment Administration

5.4.1. Premedication for Study Treatment

All patients must receive 325 to 650 mg of acetaminophen/paracetamol (orally [PO] or IV), 10 mg IV dexamethasone, and 25 to 50 mg diphenhydramine (IV or PO) (equivalent drugs of similar drug classes is also acceptable) approximately 30 min before each infusion of MIRV. If individual patients require more intensive treatment to prevent infusion-related reactions (IRRs), investigators may modify the regimen accordingly. An antiemetic medication (eg, 5-HT₃ serotonin receptor antagonists such as palonosetron, granisetron or ondansetron or appropriate alternatives) is recommended before each MIRV dose and may be used any time at the discretion of the treating physician.

5.4.2. Prophylactic use of Eye Drops

5.4.2.1. Corticosteroid Eye Drops

All patients will be mandated to use corticosteroid eye drops as prescribed by the treating physician unless the risk outweighs the benefit as per the ophthalmologist/physician. All patients will be instructed to self-administer 1% prednisolone (Pred Forte® or generic equivalent) 6 times daily on Days -1 to 4 and 4 times daily (QID) on Days 5 to 8 of each cycle during the study. For

Document ID: CLIN-00067	Title: IMGN853-0419 Clinical Study Protocol	Version: 2.0
Legacy ID: 26587		Approved Date: 12/22/202

individual patients who cannot tolerate the preservative contained in 1% prednisolone, other corticosteroid eye drops may be substituted (eg, difluprednate 0.05%; Durezol®) and administered on Days -1 to 8 of each cycle at a frequency prescribed by the ophthalmologist. If prednisolone eye drops cannot be obtained, alternate steroid eye drops are acceptable.

5.4.2.2. Lubricating Artificial Tears

Patients will be mandated to use lubricating artificial tears on a daily basis (as directed by the product label or the treating physician). Preservative-free lubricating drops are recommended. Patients should be advised to wait at least 15 minutes after corticosteroid eye drop administration before instilling lubricating eye drops.

5.4.3. Preparation and Administration of Mirvetuximab Soravtansine

5.4.3.1. Calculation for Adjusted Ideal Body Weight

The total dose of MIRV is calculated based on each patient's AIBW using the following formula:

Adjusted Ideal Body Weight (AIBW)

$$\text{AIBW} = \text{IBW}^1 + 0.4 (\text{Actual weight} - \text{IBW}^1)$$

Where:

Ideal Body Weight (IBW)

$$\text{IBW}^1 \text{ (female)} = 0.9\text{H}^1 - 92$$

¹H=height in cm; W=weight in kg)

The weight used for calculation should be obtained before study drug administration on C1D1 (-14 days). Dosing may be modified per institutional standard of care for changes in body weight on subsequent cycles. Dosing must be modified for significant ($\geq 10\%$) changes in body weight (not influenced by weight gain or loss attributed to fluid retention).

5.4.3.1.1. Preparation

MIRV is an experimental anticancer drug, and, as with other potentially toxic compounds, caution should be exercised when handling this compound. It is recommended that gloves and protective garments be worn during preparation. The desired amount of drug should be withdrawn from the vial(s) and diluted using 5% dextrose to a final concentration as outlined in the Pharmacy Manual.

Note: MIRV is incompatible with saline (0.9% sodium chloride). Therefore, dilutions should be made using 5% dextrose. Infusion bags must be labeled with the protocol number, patient number, storage temperature, dose, and volume of MIRV filtered into the bag, or labeled according to institutional protocol. Once the solution is prepared, the infusion bag should be stored at room temperature protected from direct sunlight, and the infusion must be completed within eight hours of preparation. Please refer to Pharmacy Manual for further details.

If necessary, MIRV from different drug lots may be mixed in a single-dose administration.

Document ID: CLIN-00067	Title: IMGN853-0419 Clinical Study Protocol	Version: 2.0
Legacy ID: 26587		Approved Date: 12/22/202

5.4.3.1.2. Administration

MIRV is administered at 6 mg/kg AIBW as an IV infusion following preparation as outlined in the Pharmacy Manual. Details on required and compatible infusion materials are also included in the Pharmacy Manual.

At C1D1 MIRV should be administered at a rate of 1 mg/min; after 30 min, the rate can be increased to 3 mg/min if well tolerated. If well tolerated after 30 min at 3 mg/min, the MIRV infusion rate may be increased to 5 mg/min. Subsequent infusions may be delivered at the tolerated rate. Therefore, the overall length of infusion will vary depending on dose and patient tolerability. After infusion, the IV line should be flushed with 5% dextrose as needed (PRN) to ensure delivery of the full dose.

Patients will be carefully observed during each infusion and vital signs are taken as outlined in the Schedule of Assessments ([Table 2](#)). Patients will remain in the clinic under observation for 4 hours after the first infusion, and for at least 1 hour after each subsequent infusion. While in the treatment area, patients are closely monitored for AEs.

5.5. Dose Modification Guidelines

Detailed MIRV dose modification guidelines are described below.

5.5.1. Treatment Criteria

In the absence of a TEAE that requires dose modification (as specified in the management guidance for a particular toxicity, see [Section 5.5.1.1](#)), a patient must meet the following criteria to receive MIRV at any cycle:

- ANC must be $\geq 1.5 \times 10^9/L$ (1,500/ μ L)
- Platelet count must be $\geq 100 \times 10^9/L$ (100,000/ μ L)
- All non-hematologic toxicities for which a causal association to study drug cannot be ruled out, must be \leq Grade 2 or returned to baseline; the exceptions to this rule being:
 - Treatment-emergent ocular disorders, which must have recovered to \leq Grade 1 or baseline
 - Treatment emergent pneumonitis which must have recovered to \leq Grade 1

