5.5.1.1. Mirvetuximab Soravtansine-Related Adverse Events

Dose modifications for MIRV-related AEs are described in [Table 3](#).

Table 3: Dose Modifications for Mirvetuximab Soravtansine-related Adverse Events

Severity Grade (CTCAE v5.0)	Dose Modifications for MIRV ^a
Hematological	
Neutropenia	
Grade 2 and Grade 3	Hold drug until ANC is $\geq 1.5 \times 10^9/L$ (1500 μL) and resume at the same dose level
Grade 4	Hold drug until ANC is $\geq 1.5 \times 10^9/L$ (1500 μL) and then resume at one lower dose level
Febrile neutropenia Grade 3 or 4 (with a single temperature reading $\geq 38.3^{\circ}C$ or a sustained temperature of $> 38^{\circ}C$ for > 1 hour)	Hold drug until ANC is $\geq 1.5 \times 10^9/L$ (1500 μL) and then resume at one lower dose level
Thrombocytopenia	
Grade 2 and Grade 3	Hold drug until PLT count is $\geq 100 \times 10^9/L$ (100,000/ μL) and resume at same dose level
Grade 3 associated with clinically significant bleeding that requires transfusion therapy and Grade 4	Hold drug until PLT count is $\geq 100 \times 10^9/L$ (100,000/ μL) and then resume at one lower level
Non-hematological	
Nausea and Vomiting	
Grade 3 (despite use of optimal antiemetics)	Hold drug until resolved to \leq Grade 1, then resume at one lower level
Grade 4	Permanently discontinue
Diarrhea	
Grade 3 (despite use of optimal antidiarrheal treatment)	Hold drug until resolved to \leq Grade 1, then resume at one lower level
Grade 4	Permanently discontinue
Ocular Disorders	Refer to Section 5.5.2
Noninfectious Pneumonitis	Refer to Section 5.5.3
Infusion-related Reactions	Refer to Section 5.5.5

Table 3: Dose Modifications for Mirvetuximab Soravtansine-related Adverse Events (Continued)

Severity Grade (CTCAE v5.0)	Dose Modifications for MIRV ^a
All Other Non-hematological Toxicities (except AEs related to underlying disease, Grade 3 fatigue, isolated symptomatic Grade 3 biochemistry laboratory abnormalities that last for < 7 days including electrolyte abnormalities that respond to medical intervention)	
Grade 3	Hold drug until resolved to \leq Grade 1, then resume at one lower level For any Grade 3 hepatic toxicity that does not resolve to baseline within 7 days, an abdominal CT scan must be performed to assess whether it is related to PD.
\geq Grade 3 Cardiac events (excluding Grade 3 hypertension)	Permanently discontinue
Grade 4 non-hematological toxicities	Permanently discontinue

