Abbreviations: AE = adverse event; ANC = absolute neutrophil count; CT = computed tomography; CTCAE = common terminology criteria for adverse events; MIRV = mirvetuximab soravtansine; PD = progressive disease; PLT = platelets.

^a Failure to meet retreatment criteria within 1 cycle (21 days) after the missed dose due to insufficient recovery from a treatment-related toxicity will result in treatment discontinuation unless otherwise specified in the management guidance for a particular toxicity.

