5.5.2.1. Monitoring and Preventive Measures

In early dose escalation of Study IMGN853-0401, a relationship was observed between MIRV plasma exposure and likelihood of an ocular event and response. Exposure-response modeling suggested that a dose of 6.0 mg/kg AIBW provided adequate exposure for response while also maintaining overall exposure within a range that decreased the potential for ocular AEs. Due to the observation of ocular disorders consistent with reversible keratopathy/corneal epitheliopathy in patients treated with MIRV, ocular function will be carefully monitored. Ocular symptom assessments will be performed at baseline and at Day 1 of every cycle thereafter ([Table 2](#)). Complete ophthalmologic exams will be performed in all patients at baseline and every other cycle thereafter if there is a TEAE reported.

Patients are advised to avoid using contact lenses while on MIRV. Baby shampoo and a soft cloth should be used to clean the eyes, and a warm compress at bedtime may be used to decrease any possible inflammation on the eyelid's surface. Please refer to [Section 5.4.2.1](#) and [Section 5.4.2.2](#) for details on the prophylactic use of steroid eye drops and lubricating artificial tears. The use of UVA/UVB sunglasses is recommended in full daylight during the study. The use of temporary lower punctal plugs to increase lubrication of the eyes is optional if lubricating artificial tears and corticosteroid eye drops are not sufficient. If patients report signs or symptoms of ocular disorders, including, but not limited to, blurred vision or eye irritation, the management and dose modification guidelines outlined in [Table 5](#) should be followed.

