5.5.2.2. Management and Dose Modification Guidelines

If a patient develops ocular symptoms of any grade, the patient is required to have a complete examination by an ophthalmologist. If a patient develops \geq CTCAE Grade 2 ocular symptoms, treatment with MIRV must be interrupted. Treatment should not be interrupted solely for Grade 2 ocular signs (eg, Grade 2 keratopathy) unless they are also associated with Grade 2 ocular

symptoms. Treatment with MIRV may resume if ocular symptoms improve to Grade 1 or baseline within 28 days of the next scheduled MIRV dose (refer to [Table 5](#) for details). If ocular symptoms last longer than 28 days, resumption of MIRV, with or without dose reduction, may be considered for those patients who have experienced clinical benefit if agreed upon between the Sponsor and the Investigator. Subsequent eye examinations will be scheduled to occur in every other cycle going forward, from the time that the AE was initially reported and at either the End of Treatment (EOT) Visit or 30-Day Follow-up Visit after treatment discontinuation, even if the results of the patient's ocular exam show no obvious clinical findings. Management of treatment-emergent ocular AEs with inflammatory characteristics should include corticosteroid eye drops and/or other measures as indicated by an ophthalmologist.

Table 5: Management of Ocular Symptoms

Severity Grade (CTCAE v5.0)	Management	Guidelines for MIRV Dose Modifications
Grade 1	Complete eye exam as outlined in Schedule of Assessments (Table 2) Monitor for worsening symptoms	Continue MIRV dosing
Grade 2	Complete eye exam as outlined in Schedule of Assessments (Table 2) Repeat complete exam as clinically indicated Patients should have weekly symptomatic ocular assessments by the Investigator until the symptoms resolve to Grade 1 or baseline or are deemed to be irreversible by the Investigator	Hold MIRV dosing until AE has resolved to Grade 1 or better Patients with ocular symptoms lasting < 14 days may be allowed to resume MIRV at the same dose level Patients with ocular symptoms lasting \geq 14 days but no more than 28 days may resume MIRV at one lower dose level Recurrence of Grade 2 toxicity on subsequent cycles despite best supportive care will require a MIRV dose reduction of one dose level

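### Section 5.5.1 bars dosing for a new isolated Grade 2 ocular sign, while Section 5.5.2.2 says not to interrupt for one

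*Protocol*

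**What the plan says.** Protocol Section 5.5.1 (Treatment Criteria) opens with a condition, "In the absence of a TEAE that requires dose modification" under the toxicity-specific guidance, and then lists what a patient must satisfy to be dosed at any cycle. Non-hematologic toxicities possibly caused by study drug may be up to Grade 2 or at baseline. Two exceptions are stricter, and one of them is "Treatment-emergent ocular disorders, which must have recovered to" Grade 1 or lower, or baseline. The bullet does not separate signs from symptoms.

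Section 5.5.2.2 does separate them. Symptoms of Grade 2 or higher require interruption. For signs it says "Treatment should not be interrupted solely for Grade 2 ocular signs (eg, Grade 2 keratopathy", with an exception when Grade 2 symptoms accompany them.

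Three cross-references bear on which rule was meant:

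- Table 3 (Section 5.5.1.1), in its row for ocular disorders, says "Refer to Section 5.5.2".
- Section 5.5.2.1 directs the site to Table 5 "If patients report signs or symptoms of ocular disorders, including, but not limited to, blurred vision or eye irritation".
- Table 5 is titled and graded for symptoms, and its Grade 1 row says "Continue MIRV dosing".

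**The concern.** The two sections give opposite instructions for the same patient at the same visit. Section 5.5.1 uses the stronger verb (must) and applies at every cycle. Section 5.5.2.2 is more specific but says only should not, and it does not mention the Section 5.5.1 criteria.

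A site that follows Section 5.5.1 to the letter withholds drug from a patient whom Section 5.5.2.2 says to keep treating. If the sign does not resolve, the hold can become a discontinuation. Table 3 footnote a ends treatment upon "Failure to meet retreatment criteria within 1 cycle (21 days) after the missed dose due to insufficient recovery from a treatment-related toxicity", unless the guidance for that toxicity says otherwise. Whichever rule a site follows, it departs from a written instruction. About 75 centers are planned, so different sites may resolve the conflict differently.

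**Working it through.** No sample size, power or alpha figure is involved. The check applies both rules to one test patient and then counts doses.

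**Test patient.** New Grade 2 keratopathy, not present at baseline; ocular symptoms Grade 0 or 1; causal link to MIRV not excluded; a dose is due.

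1. *Is keratopathy an ocular disorder in the protocol's terms?* Yes. Section 5.5.2.1 refers to "ocular disorders consistent with reversible keratopathy/corneal epitheliopathy in patients treated with MIRV", and it also speaks of signs as well as symptoms of ocular disorders. The Section 5.5.1 bullet therefore cannot be confined to symptoms.
2. *Does the lead-in to Section 5.5.1 switch the criteria off?* No. It yields only to an adverse event that requires dose modification. Section 5.5.2.2 requires none for an isolated Grade 2 sign, so the criteria apply.
3. *Does the patient meet the ocular criterion?* No. Grade 2 exceeds Grade 1, and the sign is new, so the baseline alternative does not help. Result under Section 5.5.1: no dose.
4. *What does Section 5.5.2.2 say?* Do not interrupt for this sign alone. Result: dose.
5. *Does any sentence give Section 5.5.2.2 precedence?* None was found. The clause deferring to toxicity-specific guidance in Table 3 footnote a and Section 5.5.6 qualifies the 21-day discontinuation rule, not the Section 5.5.1 criteria.

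**Dose count if the sign persists.** Inputs: cycle length 21 days (Q3W schedule); the 21-day limit after a missed dose (Table 3 footnote a). Let the dose be due on day D on an undelayed schedule, so the last dose was on day D − 21, and let the sign still be Grade 2 on day D + 21.

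| | Day D | Day D + 21 | Doses |
|---|---|---|---|
| Section 5.5.2.2 | given | given | 2 |
| Section 5.5.1, literal | withheld | withheld; 21-day limit reached | 0 |

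Difference: 2 − 0 = 2 doses. Time from the last dose to the limit: (D + 21) − (D − 21) = 21 + 21 = 42 days.

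**Does the ocular recovery window help?** The 28-day window in Section 5.5.2.2 is worded for symptoms, so as written it does not extend the 21 days for an isolated sign. Section 5.5.6 does leave a way out: treatment may continue in a patient with clinical benefit if the Sponsor and Investigator agree.

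**The case against.** The strongest reply is that the protocol already answers this case. Section 5.5.2.2 names the toxicity, the grade and the action. Section 5.5.1 points to Section 5.5.1.1, where Table 3 sends ocular disorders to Section 5.5.2. The per-cycle ocular check in Section 7.9.1 and Schedule of Assessments footnote l holds drug only for symptoms above Grade 1. Post-baseline eye examinations are prompted by ocular events, so a site that finds a new sign will probably already be working from Section 5.5.2.2. All of this stands as evidence of intent. None of it removes the must in Section 5.5.1.

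A second reply is that the lead-in should not be read so literally. Pneumonitis of Grade 2 or higher always requires a hold or discontinuation (Table 6), so a literal lead-in would leave the neighboring pneumonitis bullet with nothing to do. Both bullets may have been meant as thresholds for resuming after a managed event. That is a reasonable reading of purpose, but the text states the criteria for any cycle and does not limit them to resumption.

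Third, discontinuation is a remote outcome. A site would have to set Section 5.5.2.2 aside on two dosing dates. The instruction not to interrupt could also count as toxicity guidance that displaces footnote a, and Section 5.5.6 adds a Sponsor-agreed route. This is fair and limits the harm. The literal error also withholds drug, so it adds no ocular toxicity.

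Fourth, Section 5.5.2.1 sends reported signs to Table 5, whose Grade 2 row holds dosing, so amending Section 5.5.1 alone might not be enough. But Table 5 sits under the Section 5.5.2.2 text and is titled for symptoms. Once Section 5.5.1 defers to Section 5.5.2.2, the explicit sentence on signs governs.

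The case is not far-fetched. The protocol itself uses Grade 2 keratopathy as its example, and ocular symptoms of any grade trigger a full ophthalmologist examination. Blurred vision was reported in 40% of MIRV patients in the earlier Phase 3 study (Section 1.5.2). That is not a rate of isolated Grade 2 signs, but it indicates that such examinations will not be rare.

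**Conclusion.** The concern holds. For a new Grade 2 ocular sign without Grade 2 symptoms, Section 5.5.1 as written forbids a dose that Section 5.5.2.2 says not to withhold. The intended rule can be inferred and is almost certainly Section 5.5.2.2, so the defect is in the wording of Section 5.5.1.

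The 2-dose difference describes one patient. It assumes an undelayed schedule, a sign that persists for 21 days after the due date, and a site that reads Section 5.5.1 literally. The number of such patients cannot be estimated from the documents. The correction should be made, but the point does not bear on the response-rate analysis.

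**What to change.** Add to the ocular bullet in Section 5.5.1: *except isolated Grade 2 ocular signs without Grade 2 or higher ocular symptoms, for which Section 5.5.2.2 applies.* Isolated signs of Grade 3 or higher stay barred under Section 5.5.1, and no other section needs to change.

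The cost is one phrase in one bullet and a clarification letter to sites. It adds no visit, procedure or data item.
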